PRIMARY OBJECTIVE	
 1. To determine the safety and tolerability of a single or 3 consecutive daily 1g doses of Euphorbia kansui extract powder, measured and prepared as tea, in HIV+ ART-suppressed individuals. 2. To determine the immunologic effect of a single or 3 consecutive daily 1g doses of Euphorbia kansui extract powder, measured and prepared as tea, in HIV+ ART-suppressed individuals.
SECONDARY OBJECTIVES	
 3. To determine the effect of a single or 3 consecutive daily 1g doses of Euphorbia kansui extract powder, measured and prepared as tea, on latent HIV in HIV-infected ART-suppressed individuals.
NUMBER OF PARTICIPANTS	N=8 total (The first N=2 participants will receive 1 dose for a total of 1 g; the final N=6 participants will receive 3 consecutive daily doses for a total of 3 g of Euphorbia kansui extract powder prepared as tea during the study period). Following enrollment of the first 2 participants, an interim analysis will be conducted to review all study data to determine if additional participants are needed to accomplish the study purpose, and if so, if enrollment should continue at the same

	
or a higher dose (i.e., next cohort).

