PLANNED INTERIM ANALYSES	During the study, safety will be monitored by a Safety Monitoring Committee (SMC), which will be led by an HIV specialist. The SMC will review all study procedures before the initiation of the study. They will have the full and final authority to stop the study for any safety concern at any point. Given the unknown safety profile of Euphorbia kansui , the first participant in each dosing level will complete 5 days of study prior to any further participants commencing the study. The decision to proceed with further drug administration will be taken by the Principal Investigators, taking into consideration clinical and laboratory adverse events. The decision to proceed with the next dosing level will be taken by the SMC. Specifically, dosing will be stopped and the SMC will be notified if one Grade 4 or two Grade 3 drug related adverse events or laboratory abnormalities are reported, if a participant develops virologic failure (defined as any HIV-1 RNA levels >200 copies/mL or a single HIV-1 RNA level >1000 copies/mL), becomes pregnant or initiates breastfeeding, or is required to initiate one of the prohibited concomitant medications listed in section 7.1. If stopping/pausing criteria are not met, the remainder of the dosing cohort will be enrolled/dosed the subsequent week. The study will proceed to the next dosing level provided the

	stopping/pausing criteria are not met. A University of Utah Department of Medicine faculty member who is not otherwise involved in the study and who will not communicate with the study investigators regarding any aspect of the SMC reports will prepare the monitoring reports. The SMC will review accrual, adverse events summaries, CD4+ T-cell counts and HIV RNA levels/suppression over time, off-study rates and completeness of follow-up, by dose cohort.

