Given that the purpose of studying kansui in this study is to evaluate whether it can reactivate HIV from latently infected cells, there is a risk that taking kansui for up to 3 days could lead to transient loss of viral suppression and subsequent development of resistance to the participant's current antiretroviral therapy. However, given the short duration of kansui administration and the predicted small increases in plasma viremia as a result of kansui, we believe that these risks will be low. Nonetheless, as per protocol with other currently studied latent reversing agents (LRAs), we will perform frequent plasma HIV RNA monitoring (screening, every dosing day, each 24-hour follow-up, and days 31 and 132) and even more frequent monitoring of the research-based reservoir measurements of cell-associated HIV DNA and RNA (see section 9.1 below). In addition, we will only enroll participants for whom alternative ART regimens are available in the event that their previously effective regimens are compromised. Finally kansui treatment will be discontinued if the participant has any two consecutive plasma HIV RNA levels levels >200 copies/mL, or any single plasma HIV RNA level >1000 copies/mL. These values would be above the levels predicted to be seen with HIV reactivation with most current latent reactivating agents and are safety stopping criteria currently used for other HIV latent reactivating agent trials, e.g., the AIDS Clinical Trials

Group (ACTG 5336) trial, evaluating the role of Sirolimus on immune activation and the latent reservoir in chronic HIV-infected, ART-suppressed individuals.

Reproductive risks

Given the unknown reproductive risks associated with kansui as tested scientifically, and its use in traditional Chinese medicine as an abortifacient,⁸ women of childbearing potential must have a negative serum pregnancy test in the medical workup for study entry and excluded from participation if pregnant. All participants must agree to use two forms of contraception throughout the study period and up to 90 days after the last dose of kansui (to account for the male sperm cycle). Women (or female partners of male study participants) must not breastfeed during the study period and up to 90 days after the last dose of kansui.

Confidentiality

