10.4 Criteria for Discontinuation

Safety will be monitored by the dedicated SMC, led by a qualified HIV specialist in the University of Utah Department of Medicine (see Section 13 below). The SMC will have full and final authority to stop the study at any point for safety concerns. Given the unknown safety profile of *Euphorbia kansui*, the first participant in each dosing level will complete 5 days of study prior to any further participants commencing the study. The decision to proceed with further drug administration will be taken by the Principal Investigator, taking into consideration clinical and laboratory adverse events. The decision to proceed with the next dosing level will be taken by the SMC. Specifically, dosing will be paused and the SMC will be consulted if one Grade 4 or two Grade 3 drug related adverse events or laboratory abnormalities are reported.

In addition, since there is currently insufficient data demonstrating the effect of kansui on antiretroviral therapy or other concomitant medications (and vice versa), we will evaluate serum HIV-1 RNA levels using standard clinical assays within each dosing cohort prior to dose escalation. HIV RNA measures will be collected on the initial dosing day(s) (Day 1 for Cohort 1, Days 1-3 and 102-104 for Cohort 2), at the 24-hour post dosing follow-up visits on Day 2 (for Cohort 1) and Days 4 and 105 (for Cohort 2), and on Day 31 and 132. This is to safeguard against the potential risk of virologic failure and/or the development of resistance due to sub-therapeutic antiretroviral therapy drug levels in study participants.

Specifically, safety discontinuation criteria will include:

1. Any serious adverse event assessed as at least possibly related to study treatment:
 - a. Any Grade 4 drug-related adverse event or laboratory abnormality
 - b. Two Grade 3 drug-related adverse event or laboratory abnormality
2. Virologic failure (defined as any two consecutive HIV-1 RNA levels >200 copies/mL or a single HIV-1 RNA level >1000 copies/mL). These values would be above the levels predicted to be seen with HIV reactivation with most current latent reactivating agents and are safety stopping criteria currently used for other HIV latent reactivating agent trials, e.g., the AIDS Clinical Trials Group (ACTG 5336) trial, evaluating the role of Sirolimus on immune activation and the latent reservoir in chronic HIV-infected, ART-suppressed individuals.
3. Pregnancy or breastfeeding

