4. Requirement for prohibited concomitant medications (see section 7.1)
5. Clinical reasons believed life threatening by the physician, even if not addressed in the toxicity section of the protocol

The specific adverse events that will be solicited include: diarrhea, gastrointestinal irritability, gastrointestinal bleeding, headache, and symptoms of dehydration (light-

headedness, tachycardia). For the most likely expected reported adverse event, diarrhea, we will strictly adhere to established toxicity grading used by the National Cancer Institute for chemotherapy-induced diarrhea.^{39,40}

Grade	Description
1	Increase of fewer than four stools per day over baseline
2	Increase of four to six stools per day over baseline
3	Increase of seven or more stools per day over baseline; incontinence; hospitalization indicated
4	Life-threatening consequences; urgent intervention indicated
5	Death

** Based on information from National Cancer Institute, 2010.*

If stopping/pausing criteria are not met, the remainder of the dosing cohort will be enrolled/dosed the subsequent week. The study will proceed to the next dosing level provided the stopping/pausing criteria are not met. A University of Utah Department of Medicine faculty member who is not otherwise involved in the study and who will not communicate with the study investigators regarding any aspect of the SMC reports will prepare the monitoring reports. The SMC will review accrual, adverse events summaries, CD4+ T-cell counts and HIV RNA levels/suppression over time, off-study rates and completeness of follow-up, by dose cohort.

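### No repeat HIV RNA is ordered after a first value of 201-1000 copies/mL, so the two-consecutive rule can be undecided at the sentinel and escalation steps, and the synopsis omits the confirmation requirement

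*Combined protocol and SAP*

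**What the plan says.** **The rule.** Section 10.4 gives, as a safety discontinuation criterion, "Virologic failure (defined as any two consecutive HIV-1 RNA levels >200 copies/mL or a single HIV-1 RNA level >1000 copies/mL". Section 2.1 states the same rule for the individual participant: "kansui treatment will be discontinued if the participant has any two consecutive plasma HIV RNA levels" above 200, or has one above 1000. The synopsis (Planned Interim Analyses) lists virologic failure among the events that stop dosing and trigger SMC notification, but there it is "defined as any HIV-1 RNA levels >200 copies/mL or a single HIV-1 RNA level >1000 copies/mL".

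**The sentinel step.** Under Section 10.4, "the first participant in each dosing level will complete 5 days of study prior to any further participants commencing the study". The Principal Investigator then decides on further dosing. If no criterion is met, "the remainder of the dosing cohort will be enrolled/dosed the subsequent week".

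**The escalation step.** "The study will proceed to the next dosing level provided the stopping/pausing criteria are not met" (Section 10.4), with the decision assigned to the SMC. The timing is described in several ways. The synopsis says "Following enrollment of the first 2 participants, an interim analysis will be conducted to review all study data", and elsewhere places the analysis after Cohort 1 is complete. Section 4.1 has safety data through week two going to the SMC. Section 13 puts the meeting after cohort completion and at least two weeks after the last dose. Section 10.4 adds that HIV RNA will be evaluated within each cohort before escalation.

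**The draws.** Section 10.4 schedules standard HIV RNA on dosing days, on Day 2 for Cohort 1, and on "Days 4 and 105 (for Cohort 2), and on Day 31 and 132". The events tables add screening, baseline and Day 88, and show no procedures in washout (Days 32-87).

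**The concern.** A rule that needs two consecutive values works only if the second value is obtained in time for the decision it informs. Here the second value depends entirely on the visit calendar. Where the calendar has a long gap, or ends, a first result of 201-1000 is neither confirmed nor refuted, and the criterion counts as not met by default.

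Two decisions could be taken in that state: starting the next participant after the sentinel, and moving from one dose to three. Section 2.1 names transient loss of suppression and resistance to current ART as risks, and Section 10.4 says the HIV RNA schedule is there to guard against them. Site staff also hold two versions of the rule, which give opposite instructions for the same lone result.

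**Working it through.** The plan gives no figure to reproduce, so the check compares the rule with the calendar.

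**Step 1. The two versions of the rule.** Take example results in copies/mL.
- 39, 39, 500: not failure under 10.4; failure under the synopsis.
- 39, 39, 500, 500: failure under both.
- 39, 39, 1001: failure under both.

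They differ only for a lone value of 201-1000. In the synopsis the second limb does no work, because any value above 1000 is already above 200. That suggests the confirmation requirement was left out by mistake.

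**Step 2. Wait for the next scheduled value.** Days are from Section 10.4 and the events tables. Wait = next scheduled day minus day of first rise.

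| Cohort | First value of 201-1000 | Next draw | Wait |
|---|---|---|---|
| 1 | Day 2 | Day 31 | 31 - 2 = 29 days |
| 1 | Day 31 | none | none |
| 2 | Day 2 or 3 | next day | 1 day |
| 2 | Day 4 | Day 31 | 31 - 4 = 27 days |
| 2 | Day 31 | Day 88 | 88 - 31 = 57 days |
| 2 | Day 88 | Day 102 | 102 - 88 = 14 days |
| 2 | Day 102, 103 or 104 | next day | 1 day |
| 2 | Day 105 | Day 132 | 132 - 105 = 27 days |
| 2 | Day 132 | none | none |

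Within a three-day course the daily draws supply the second value. The gaps come after the course. Each Cohort 2 participant has one placebo course, so one set of the Cohort 2 rows follows placebo, not kansui.

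**Step 3. Escalation.** The earliest SMC meeting is last dose + 14 days, which is 1 + 14 = Day 15 for the second Cohort 1 participant. By then that person has one post-dose value (Day 2), and the next is 31 - 15 = 16 days away. No post-dose pair can exist. A pair could form only if the pre-dose Day 1 value were also above 200, which is unlikely given entry at under 40 copies/mL. If the first participant started *s* days earlier, that person is at Day 15 + *s*, and has a Day 31 value only if *s* is at least 16. If the meeting instead follows Day 31, a first Day 2 rise is resolved, but a first Day 31 rise has no later draw.

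**Step 4. Sentinel.** In Cohort 1 the sentinel's only post-dose value by Day 5 is Day 2, so no post-dose pair is possible. In Cohort 2, Days 2, 3 and 4 are available. Only a first rise on Day 4 is left open, and it bears on kansui only if the sentinel was randomized to kansui first. Taking the subsequent week as Days 6-14 (an assumption), other participants could start 31 - 14 = 17 to 31 - 6 = 25 days before the sentinel's Day 31 draw.

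**Step 5. Does any other text supply the repeat?**
- Section 13 has the team assess participants with an unconfirmed HIV RNA result, but orders no draw and sets no time limit.
- Section 9.5.1 (real-time viral load) and Section 10.3 (48-hour reporting) speed up a result; they do not create a second one.
- Section 11.1 follows an abnormal parameter only after withdrawal from treatment for an adverse event.
- The early withdrawal visit includes HIV RNA, but a lone 201-1000 value does not trigger that visit.

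**The case against.** The strongest reply is that people, not the calendar, make both decisions. The Principal Investigator weighs clinical and laboratory events before further dosing, the SMC sees HIV RNA by cohort and can stop the study at any point, and the team looks at unconfirmed values. Section 10.4 also places evaluation of HIV RNA before escalation and includes Day 31 among the draws, which, with the completion wording in the synopsis and Section 13, favours a meeting after Day 31. Not stopping on one modest value is also what a two-consecutive rule is meant to do.

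Most of this stands. It makes the escalation gap possible rather than certain, and it makes harm less likely. It does not remove the gap: Section 4.1 and the two-week minimum in Section 13 still permit the early meeting, and none of these people is told to obtain the second sample.

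A further reply is that 10.4's pause sentence names only Grade 3 and 4 events, while virologic failure sits in the discontinuation list and Section 2.1 applies it per participant. That the rule also gates other participants is therefore a reading, through the sentence on stopping and pausing criteria. It is a reasonable one, since the synopsis puts virologic failure in the same list as the graded events.

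A reader might infer more than the documents support:
- *That the synopsis sets a different threshold.* The 200 and 1000 cut-offs are identical; only the confirmation requirement differs.
- *That late plasma rises are to be expected, because Section 1 reports Ing B effects to about 30 days in ART-suppressed monkeys.* For ART-treated animals that section specifies reactivation from resting CD4+ T cells. It does not show plasma values of 201-1000 under ART, and Ing B is a different, semi-synthetic agent.

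**Conclusion.** The concern holds as a gap in the decision rule together with a conflict between sections. The synopsis and Section 10.4 give opposite instructions for a lone value of 201-1000, and no section orders the repeat that the two-consecutive rule needs.

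The consequence is clearest in Cohort 1. At the earliest permitted escalation review the second participant has one post-dose value, so the criterion cannot be met by a post-dose pair. At the sentinel step the unresolved interval is 29 days (Cohort 1, Day 2) or 27 days (Cohort 2, Day 4, sentinel on kansui). First rises on Day 31 in Cohort 1 or Day 132 in Cohort 2 have no follow-up draw; no further dose is then at stake for that participant, only the follow-up of a possible loss of suppression.

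The number of participants affected cannot be estimated. The documents give no rate of such values, and Sections 2.1 and 10.4 say the limits lie above what is predicted for most agents of this kind. A reader might apply a guessed rate to all eight participants or to every uncovered draw. That would overstate the problem, because it counts final visits and placebo-period draws alongside the decisions that matter. The conclusion rests on the earliest timing the text allows and on the schedule as written. It warrants a correction; it does not show that escalation would be unsafe.

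**What to change.** 1. Align the synopsis with Sections 2.1 and 10.4: two consecutive values above 200, or one above 1000 copies/mL.
2. In Section 10.4, require a repeat standard HIV RNA within about 1-2 weeks of a first post-dose value of 201-1000 whenever no scheduled draw falls in that window, including during washout and after the final visit. State that this repeat counts as the consecutive value.
3. Have two decisions await the result: the start of the next participant after the sentinel, and the SMC escalation decision. Doses within a three-day course need no hold, because the next day's draw already supplies the second value.

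With a 7-day repeat, a Cohort 1 Day 2 rise is settled by 2 + 7 = Day 9, before the earliest SMC meeting on Day 15. With a 14-day repeat it is settled by 2 + 14 = Day 16, one day after that meeting, which is why item 3 is needed.

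The cost is protocol wording, an occasional unscheduled blood draw (with an exception to the no-procedures washout), and a delay of up to about 2 weeks when triggered. The Section 10.4 stopping limits and the dosing regimen do not change.

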11 DISCONTINUATION AND REPLACEMENT OF PARTICIPANTS

11.1 Early Discontinuation of Study Drug

A participant may be discontinued from study treatment at any time if the participant or the investigator feels that it is not in the participant's best interest to continue. The following is a list of possible reasons for study treatment discontinuation:

- Participant withdrawal of consent
- Participant is not compliant with study procedures
- Adverse event that in the opinion of the investigator would be in the best interest of the participant to discontinue study treatment
- Protocol violation requiring discontinuation of study treatment
- Lost to follow-up
- Sponsor request for early termination of study
- Positive pregnancy test or breastfeeding (females)

If a participant is withdrawn from treatment due to an adverse event, the participant will be followed and treated by the Investigator until the abnormal parameter or symptom has resolved or stabilized.

All participants who discontinue study treatment should come in for an early discontinuation visit as soon as possible and then should be encouraged to complete all remaining scheduled visits and procedures.

All participants are free to withdraw from participation at any time, for any reason, specified or unspecified, and without prejudice.

Reasonable attempts will be made by the investigator to provide a reason for participant withdrawals. The reason for the participant's withdrawal from the study will be specified in the participant's source documents (refer to early termination procedures).

11.2 Withdrawal of Participants from the Study

A participant may be withdrawn from the study at any time if the participant, the investigator, or the Sponsor feels that it is not in the participant's best interest to continue.

11.3 Replacement of Participants

Participants who withdraw from the study treatment before last day of study drug dosing (i.e., Day 1 for Cohort 1, Day 104 for Cohort 2) will be replaced by another enrolled participant to maintain total study numbers.

The CRF will document the reason for the withdrawal and date of withdrawal. Date of withdrawal will be documented as the date of last study drug treatment, not the date that the decision to withdraw treatment was made.

Participants will be followed after withdrawal from the study for 3 calendar days after cessation of treatment. All adverse events during that period will be reported.

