10.2.1 Serious Adverse Experience Reporting

The study site will document all SAEs that occur (whether or not related to study drug) per the University of Utah IRB Guidelines. The collection period for all SAEs will begin after informed consent is obtained and end after procedures for the final study visit have been completed.

In accordance with the standard operating procedures and policies of the local Institutional Review Board (IRB), the site investigator will report SAEs to the IRB.

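### Section 11.3's 3-day adverse-event period and last-dose withdrawal date conflict with 9.2.7, 10.3 and 11.1, and could shorten safety reporting for participants who withdraw

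*Combined protocol and SAP*

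**What the plan says.** Section 11.3 deals with replacement and withdrawal. It states "Participants will be followed after withdrawal from the study for 3 calendar days after cessation of treatment" and continues "All adverse events during that period will be reported". On dating it states "Date of withdrawal will be documented as the date of last study drug treatment, not the date that the decision to withdraw treatment was made". Anyone who withdraws from treatment before the last dosing day (Day 1 in Cohort 1, Day 104 in Cohort 2) "will be replaced by another enrolled participant to maintain total study numbers".

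Other sections set different end points:

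- **11.1**: for a participant taken off treatment because of an adverse event, "the participant will be followed and treated by the Investigator until the abnormal parameter or symptom has resolved or stabilized". Everyone who stops treatment attends an early discontinuation visit and "then should be encouraged to complete all remaining scheduled visits and procedures".
- **9.2.7**: adverse-event information is collected for the whole study.
- **10.3**: all participants are followed for adverse events over the whole study period. Grade 3 or 4 events that require permanent discontinuation are followed until they fall to Grade 2 or lower.
- **10.2.1**: collection of serious events starts after consent and is to "end after procedures for the final study visit have been completed".
- **9.1.5**: the early withdrawal visit records adverse events, with no day limit.

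Safety and tolerability is the primary endpoint (synopsis and 3.1). Section 14.3 tabulates adverse events by dosing cohort and does not say how withdrawn or replaced participants are counted.

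**The concern.** The documents give a site two answers to one question: how long are adverse events reported for someone who stops early? Under 11.3 the answer is three days from the last dose. Under 9.2.7, 10.3 and 11.1 it is the rest of the study, or until the event settles. The same safety table could then combine completers observed for about four weeks after dosing with withdrawn participants observed for three days, with nothing in the table to show it.

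The dating rule adds a second problem. If the recorded withdrawal date is always the last-dose date, the database cannot show how long a person was on study, so the length of observation cannot be recovered later.

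The data feed decisions as well as the final summary. Section 4.1 bases escalation on safety data through week two, and section 13 has the Safety Monitoring Committee meet no earlier than two weeks after the last dose. A three-day period cannot supply that for a withdrawn participant.

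**Working it through.** The plan gives no figure to reproduce here. The check is a comparison of text plus day counts on the plan's own calendar.

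**Calendar check.** 14 + 31 = 45 days (Cohort 1) and 14 + 132 = 146 days (Cohort 2). Days 32 to 87 inclusive are 87 − 32 + 1 = 56 washout days. All three match the stated durations, so the day numbering is read correctly.

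**Do the rules reach the same person?** Section 11.1 is headed as discontinuation of study drug. The 3-day sentence in 11.3 speaks of withdrawal from the study. But 11.3 opens with participants who withdraw from treatment, starts its three days when treatment ceases, and dates withdrawal by the last dose. Someone who stops drug for an adverse event after the first or second dose of a Cohort 2 phase falls under both sections.

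**Length of the period.** Period end = last-dose day + 3. Uncovered days = scheduled end of phase − period end. Post-dose days = scheduled end of phase − last-dose day.

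| Case | Last dose | Period ends | Phase ends | Post-dose days | Uncovered |
|---|---|---|---|---|---|
| Cohort 1 | Day 1 | Day 4 | Day 31 | 30 | 27 (90%) |
| Cohort 2, phase 1, three doses | Day 3 | Day 6 | Day 31 | 28 | 25 (89%) |
| Cohort 2, phase 2, three doses | Day 104 | Day 107 | Day 132 | 28 | 25 (89%) |

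**Dating.** A Cohort 2 participant who completes phase 1 and decides to leave between Day 31 and Day 101 is recorded as withdrawn on Day 3. The record is early by 31 − 3 = 28 to 101 − 3 = 98 days.

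**Effect of one missed participant-event.** Because 14.3 summarises by cohort, the denominators are 2 and 6, not 8: 1/2 = 50 points in Cohort 1 and 1/6 = 16.7 points in Cohort 2. If a replaced Cohort 2 participant stays in the summary, the denominator becomes 7 and the step is 1/7 = 14.3 points. The plan does not say which applies.

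**Chance that the rule is needed.** The plan gives no withdrawal rate. As an assumption only, with an independent probability p per participant, P(at least one of n) = 1 − (1 − p)^n:

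| Assumed p | n = 6 | n = 8 |
|---|---|---|
| 5% | 26.5% | 33.7% |
| 10% | 46.9% | 57.0% |
| 20% | 73.8% | 83.2% |

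**The case against.** The strongest reply is that 11.3 sets a minimum. It contains no word such as only, does not tell anyone to discard other events, and sits alongside 9.2.7, 10.3 and the early withdrawal visit in 9.1.5, all of which collect adverse events without a three-day limit. After consent is withdrawn, further follow-up cannot be required in any case. This stands in part: loss of data is a possible consequence of 11.3, not a stated one. It does not remove the conflict, because a reader of 11.3 alone finds a fixed period and a reader of 10.3 finds another.

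The conflict with 10.2.1 is narrower. It concerns serious events only, and for a withdrawn person the final visit may be read as the early withdrawal visit.

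A reader might infer more than the documents support:

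- **That the back-dated record removes data from the analysis.** Section 14.3 does not censor at the withdrawal date. The harm shown is a wrong date, not a deletion.
- **That someone leaving during the washout, say on Day 60, loses weeks of data.** That person is recorded 57 days early (60 − 3), but has already had the Day 31 visit, and the schedule has no procedures in the washout for anyone. Scheduled adverse-event visits are lost by those who leave before Day 31 or Day 132.
- **That the summary is biased toward kansui looking tolerable.** Most reasons listed in 11.1 for stopping are not adverse events, those who stop because of one are the group that 11.1 follows longest, and a Cohort 2 participant may leave after placebo.
- **That late events are to be expected because the background reports effects at about 30 days.** Those are immune and viral effects of a semi-synthetic ingenol in macaques, not adverse events of kansui tea. Section 2.1 says that common adverse events usually occur within two hours of ingestion.

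**Conclusion.** The contradiction is real and concerns the primary endpoint. If 11.3 is applied as written, a participant who withdraws soon after the last dose of a phase has adverse-event reporting for 3 of 28 to 30 post-dose days, and the recorded withdrawal date can differ from the true one by up to 98 days. In cohorts of 2 and 6, one missed participant-event is 50 or 16.7 percentage points of a crude rate.

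The size is conditional on a withdrawal occurring and on the site following 11.3 rather than 9.2.7, 10.3 and 11.1. The direction of any error is not established, and no power or sample-size figure is affected. This is an inconsistency that should be corrected, not a demonstrated bias.

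**What to change.** 1. Reconcile 9.2.7, 10.2.1, 10.3, 11.1 and 11.3. Separate stopping treatment from leaving the study, and state one reporting period for adverse events and serious adverse events that holds in every section.
2. Record both the last-dose date and the actual withdrawal date.
3. State in 14.3 that every event recorded while a dosed participant was on study is counted, including events of participants later replaced, and is assigned to the treatment phase in which it began. Say where events that start in the washout or second screening belong.
4. Show the number dosed and the days of observation beside each adverse-event rate, so that unequal follow-up is visible.

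The length and content of clinical follow-up are for the investigators to settle. The cost is wording in six sections and one extra date field on the case report form. No visit, sample or participant is added by these statistical changes.
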